 - Wide field radiotherapy (including radioisotopes) ≤ 2 weeks prior to starting study drug unless there are ongoing side effects $>$ Grade 2.

9. Patients who are currently receiving treatment with agents that are known strong inducers or inhibitors of CYP3A4 are prohibited.
10. Enzyme inducing anti-epileptic drugs.
11. Consumption of grapefruit, grapefruit juice, pomegranates, star fruits, Seville oranges or products within 7 days prior to first dose.
12. Use of medications that are known to prolong the QT interval and/or are associated with a risk of Torsades de Pointes 7 days prior to first dose.
13. Use of amiodarone within 90 days prior to first dose.
14. Use of medications that increase serum levels of phosphorus and/or calcium.
15. Current use of therapeutic doses of warfarin sodium or any other coumadin-derivative anticoagulants. Heparin and/or low molecular weight heparins or other anticoagulants are allowed.
16. Insufficient bone marrow function
 - ANC $< 1,000/\text{mm}^3$ [$1.0 \times 10^9/\text{L}$]
 - Platelets $< 75,000/\text{mm}^3$ [$75 \times 10^9/\text{L}$]
 - Hemoglobin $< 10.0 \text{ g/dL}$
17. Insufficient hepatic and renal function
 - Total bilirubin $> 1.5 \times \text{ULN}$ (unless evidence of Gilbert's disease)
 - AST/SGOT and ALT/SGPT $> 2.5 \times \text{ULN}$
 - Serum creatinine $\geq \text{ULN}$ and/or calculated or measured creatinine clearance $< 75\% \text{ LLN}$
18. Calcium-phosphate homeostasis
 - Inorganic phosphorus outside of normal limits
 - Total and ionized serum calcium outside of normal limits
19. Clinically significant cardiac disease including any of the following:
 - Congestive heart failure requiring treatment (NYHA grade ≥ 2), LVEF $< 50\%$ as determined by MUGA scan or ECHO, or uncontrolled hypertension (refer to WHO-ISH guidelines)
 - History or presence of clinically significant ventricular arrhythmias, atrial fibrillation, resting bradycardia, or conduction abnormality
 - Unstable angina pectoris or acute myocardial infarction ≤ 3 months prior to starting study drug
 - QTcF $> 450 \text{ msec}$ (both genders)
 - History of congenital long QT syndrome
20. Pregnant or nursing (lactating) women, where pregnancy is defined as the state of a female after conception and until the termination of gestation, confirmed by a positive hCG laboratory test
21. Known positive serology for HIV, active Hepatitis B, and/or active Hepatitis C infection.

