6.1.5 Dose modification and dose delay

For patients who do not tolerate the protocol-specified dosing schedule, dose adjustments are permitted in order to allow the patient to continue the study treatment. The following guidelines need to be applied:

These changes must be recorded appropriately.

All dose modifications should be based on the worst preceding toxicity.

Following resolution of toxicity to baseline or \leq grade 1, treatment is resumed at either the same or lower doses of study drugs as per the criteria in [Table 6-3](#). If treatment is resumed at the same doses of study drugs, and the same toxicity recurs with the same or worse severity regardless of duration, doses must be reduced to the next lower dose level. If treatment is resumed at the lower doses of study drugs, and the same toxicity recurs with the same or worse severity, the patient must discontinue study treatment.

If a patient requires a dose delay of > 14 consecutive days of BGJ398 (infigratinib) from the intended day of the next scheduled dose, then the patient should be discontinued from the study treatment, unless extenuating circumstance occur and approval from Novartis is obtained.

Patients who discontinue the study for a study related adverse event or an abnormal laboratory value must be followed as described in [Section 6.1.5](#).

Table 6-2 Dose reduction table

Dose reduction			
	Starting dose level 0	Dose level - 1	Dose level - 2
BJG398	125 mg	100 mg	75 mg

A third or subsequent reduction (to 50 mg) in dose may be allowed if the patient is clearly benefiting from study treatment (i.e., stable disease, partial response, or complete response) but is experiencing adverse events that prevent continued treatment at the already reduced dose.

Table 6-3 Recommended dose modifications for BGJ398 (infigratinib) treatment

6.2 Worst Toxicity CTCAE v4.03 Grade (unless otherwise specified)	6.3 Recommended Dose Modifications any time during a cycle of therapy
Cardiac disorders	
Cardiac - Prolonged QTcF interval	

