
Serum creatinine
 
Grade 1 and Pi >5.5 mg/dL and/or tCa x Pi >55 mg²/dl² and despite phosphorus lowering therapy for at least 14 days
 
Grade 2 (> 1.5 - 3.0 x ULN)
 
Grade 2 and Pi >5.5 mg/dL and/or tCa x Pi >55 mg²/dl² and despite phosphorus lowering therapy for at least 14 days
 
Grade ≥ 3 (> 3.0 x ULN)
	
Hold dose of BGJ398 (infigratinib) until resolved to CTCAE Grade ≤ 1 or baseline
 
 • If resolved in ≤ 7 days, maintain dose level of BGJ398 (infigratinib). • If resolved in > 7 days, ↓ 1 dose level of BGJ398 (infigratinib). 
Hold dose of BGJ398 (infigratinib) until resolved to CTCAE Grade ≤ 1 or baseline
 
 • If resolved in ≤ 7 days, maintain dose level of BGJ398 (infigratinib). • If resolved in > 7 days, ↓ 1 dose level of BGJ398 (infigratinib). 
Discontinue patient from study treatment
 
Discontinue patient from study treatment.

Investigations – Hepatic	

Blood bilirubin (patients with Gilbert Syndrome these dose modifications apply to changes in direct bilirubin only)
 
Grade 2 (>1.5 – 3.0 x ULN)
 
Grade ≥ 3 (> 3.0 x ULN)
	
Hold dose of BGJ398 (infigratinib) until resolved to CTCAE Grade ≤ 1
 
 • If resolved in ≤ 7 days, maintain dose level of BGJ398 (infigratinib). • If resolved in > 7 days, ↓ 1 dose level of BGJ398 (infigratinib). 
Discontinue patient from study treatment.

6.2 Worst Toxicity CTCAE v4.03 Grade (unless otherwise specified)	6.3 Recommended Dose Modifications any time during a cycle of therapy
	Note: If CTCAE Grade 3 or 4 hyperbilirubinemia is due to hemolysis, then ↓ 1 dose level of BGJ398 (infigratinib) and continue treatment at the discretion of the Investigator.

AST or ALT Grade 3 (> 5.0 - 20.0 x ULN) without bilirubin elevation > 2.0 x ULN
 
Grade 4 (> 20.0 x ULN) without bilirubin elevation > 2.0 x ULN
	
Hold dose of BGJ398 (infigratinib) until resolved to CTCAE Grade ≤ 1 or baseline
 
 • If resolved in ≤ 7 days, maintain dose level of BGJ398 (infigratinib). • If resolved in > 7 days, ↓ 1 dose level of BGJ398 (infigratinib). 
Discontinue patient from study treatment.

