
AST or ALT and Bilirubin AST or ALT > 3.0 – 5.0 x ULN and total bilirubin > 2.0 x ULN without liver metastasis or evidence of disease progression in the liver
 
AST or ALT > 5.0 x ULN and total bilirubin > 2.0 x ULN
	
Hold dose of BGJ398 (infigratinib) until resolved to CTCAE Grade ≤ 1
 
 • If resolved in ≤ 7 days, ↓ 1 dose level of BGJ398 (infigratinib). • If resolved in > 7 days, discontinue patient from study treatment. 
Discontinue patient from study treatment.

Laboratory / Metabolic disorders	

Asymptomatic amylase and/or lipase elevation
 
Grade 3 (> 2.0 - 5.0 x ULN)
 
Grade 4 (> 5.0 x ULN)
	
 • Hold dose of BGJ398 (infigratinib) until resolved to CTCAE Grade ≤ 2. • ↓ 1 dose level of BGJ398 (infigratinib) 
Note: A CT scan or other imaging study to assess the pancreas, liver, and gallbladder must be performed within 1 week of the first occurrence of any CTCAE ≥ Grade 3 amylase and/or lipase.
 
If asymptomatic CTCAE Grade 2 elevations of lipase and/or amylase occur again at the reduced dose, patients will be discontinued permanently from study treatment.
 
Discontinue patient from study treatment

Hyperphosphatemia Serum phosphorus > 5.5 – 7.0 mg/dL
	
Maintain dose level of BGJ398 (infigratinib), but modify phosphate lowering therapy
 
Hold BGJ398 (infigratinib) dose until resolved to serum phosphorus ≤ 5.5 mg/dL

6.2 Worst Toxicity CTCAE v4.03 Grade (unless otherwise specified)	6.3 Recommended Dose Modifications any time during a cycle of therapy
Serum phosphorus >7.0 – 10.0 mg/dL despite phosphate lowering therapy Serum Pi > 10.0 mg/dL	
 • if resolved by ≤ 14 days after suspending BGJ398 (infigratinib), ↓ 1 dose level • if does not resolve within 14 days of suspending BGJ398 (infigratinib), discontinue patient from the study. Discontinue patient from the study
Hypercalcemia Serum calcium grade 2 Serum calcium ≥ grade 3	Hold BGJ398 (infigratinib) dose until resolved to grade 1 or baseline: 
 • if resolved ≤ 7 days after suspending BGJ398 (infigratinib), maintain dose level • if resolved > 7 days after suspending BGJ398 (infigratinib), ↓ 1 dose level Discontinue patient from the study
Nervous system disorders	

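### Table 6-3: AST/ALT > 3.0–5.0 x ULN with bilirubin > 3.0 x ULN meets both a stop row and a re-dose row, and the worst-toxicity rule does not expressly rank them

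*Combined protocol and SAP*

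**What the plan says.** All the relevant text is in protocol section 6.1.5, in the hepatic part of Table 6-3, unless stated otherwise.

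- **Bilirubin row.** Grade 2 (> 1.5–3.0 x ULN): hold to Grade 1 or lower, then keep the dose if resolved in 7 days or less, or reduce one level if it takes longer. The top tier, "Grade ≥ 3 (> 3.0 x ULN"), is to discontinue. Neither tier refers to AST or ALT.
- **Two qualifiers on the bilirubin row.** For "patients with Gilbert Syndrome these dose modifications apply to changes in direct bilirubin only". And "If CTCAE Grade 3 or 4 hyperbilirubinemia is due to hemolysis", the action becomes a one-level reduction with continuation at the investigator's discretion. Patients with Gilbert syndrome can be enrolled, because section 5.2 item 17 sets its bilirubin limit "unless evidence of Gilbert's disease".
- **AST/ALT alone.** These tiers apply only when bilirubin is not above 2.0 x ULN.
- **AST/ALT with bilirubin, first tier.** AST or ALT > 3.0–5.0 x ULN "and total bilirubin > 2.0 x ULN without liver metastasis or evidence of disease progression in the liver". The action is to hold to Grade 1 or lower. Then: "If resolved in ≤ 7 days, ↓ 1 dose level of BGJ398 (infigratinib"). If it takes longer than 7 days, discontinue.
- **AST/ALT with bilirubin, second tier.** AST or ALT > 5.0 x ULN with total bilirubin > 2.0 x ULN: discontinue.
- **General rule.** "All dose modifications should be based on the worst preceding toxicity" stands in the text of 6.1.5 and again in the note that closes the table. The toxicity column is headed "Worst Toxicity CTCAE v4.03 Grade (unless otherwise specified").

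**The concern.** The first combined tier has a lower bilirubin limit but no upper one, so it extends into the range where the bilirubin row already stops treatment. In that range, adding raised transaminases to a stop-level bilirubin opens a route back to treatment that the same bilirubin alone does not offer. The route is also confined to patients without liver metastasis or liver progression, that is, to those in whom liver disease is not the ready explanation. A patient with liver metastasis and the same laboratory values meets only the stop row.

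The trial is multicenter, so two sites could handle the same event differently: one stops the drug and the other resumes it at 100 mg after 125 mg, or at 75 mg after 100 mg (Table 6-2). Hepatic toxicity is documented for this drug. In study CBGJ398X2101 (section 1.2.1.2.1), two of the four dose-limiting toxicities were Grade 3 AST/ALT elevations, one of them in the 100 mg cohort. Those were transaminase events; the section does not report the combination at issue here.

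**Working it through.** The plan states no figure on this point, so the check is to set the rows side by side.

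**Inputs.** The bilirubin row and the first combined tier of Table 6-3, for a patient with AST/ALT > 3.0–5.0 x ULN, no liver metastasis or liver progression, no hemolysis and no Gilbert syndrome. There are two bilirubin bands and two recovery times, hence four cells.

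| Total bilirubin | Recovery | Bilirubin row | Combined tier | Stricter action |
|---|---|---|---|---|
| > 2.0–3.0 x ULN | ≤ 7 days | hold, same dose | hold, reduce 1 | hold, reduce 1 (combined) |
| > 2.0–3.0 x ULN | > 7 days | hold, reduce 1 | discontinue | discontinue (combined) |
| > 3.0 x ULN | ≤ 7 days | discontinue | hold, reduce 1 | discontinue (bilirubin) |
| > 3.0 x ULN | > 7 days | discontinue | discontinue | discontinue (same) |

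**Result.** The rows differ in 3 of 4 cells. In the two cells of the lower band the combined tier is stricter, as one would expect of a row for a more worrying pattern. In the third cell the order reverses.

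**Spot values (multiples of ULN).**

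- AST/ALT 4, bilirubin 2.5: meets bilirubin Grade 2 and the first combined tier.
- AST/ALT 4, bilirubin 3.5: meets bilirubin Grade ≥ 3 (discontinue) and the first combined tier (hold, with possible re-dose). The same holds at bilirubin 11, because the tier has no ceiling.
- AST/ALT 4, bilirubin 3.5, with liver metastasis: meets only the bilirubin stop row.
- AST/ALT 6, bilirubin 3.5: meets two rows, and both say discontinue.

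**Does the general rule settle it?** At AST/ALT 4 and bilirubin 3.5, bilirubin is labelled Grade 3 or higher, while AST/ALT is below the table's Grade 3 threshold of > 5.0 x ULN. Bilirubin is therefore the worse graded toxicity, and its action is to stop. That is the natural reading.

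But the combined tier is defined by multiples of ULN and carries no CTCAE grade, so it cannot be ranked on that scale, and the column header allows for exceptions. In the lower band, the only graded row met is bilirubin Grade 2. If the graded row always won, the combined tier would be overridden there too, although it is plainly meant to tighten the action. A site that lets the combined tier govern in the lower band could do the same above 3.0 x ULN.

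**The case against.** The strongest reply is that the plan already answers the question. The worst-toxicity rule appears twice, once in this table's own closing note, and it points to the bilirubin stop row. The two rows can also be applied together: the stop depends only on the laboratory value, whereas the re-dose comes later and is conditional, so once treatment has been discontinued there is nothing to resume. Most of this stands. A reader might infer that the plan has no rule bearing on the case, or that it directs sites to re-dose. The documents do not support either reading. What remains is that no sentence ranks two rows met by one event, and the combined tier's instruction to hold presupposes that treatment has not ended.

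Oversight also limits the harm. Section 13.5 provides weekly multi-institutional review of adverse events and protocol adherence, and Appendix B makes the lead investigator responsible for timely adverse event review. Section 6.1.5 requires discontinuation if the same toxicity recurs at the lower dose with the same or worse severity. These safeguards stand, but they find or contain a divergent decision rather than say which decision is correct.

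Finally, the action column is headed as recommended. That does not make divergence intended, because section 6.1.5 introduces the guidelines as ones that have to be applied.

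**Conclusion.** The overlap is real and warrants a minor safety correction. The two rows give different actions in 3 of 4 cells. The cell that matters for safety is bilirubin > 3.0 x ULN with recovery within 7 days, where one row ends treatment and the other resumes it one level lower. For a patient already at 75 mg, a further step would be a third reduction: the table's closing note ends treatment, although the note under Table 6-2 may allow 50 mg for a patient who is clearly benefiting.

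The conclusion assumes that the actions line up with the tiers in the order printed, and it covers patients without hemolysis or Gilbert syndrome. The documents give no rate for the event. That it is rare is an inference from how many conditions must coincide, so no expected count is offered. A reader might also infer a threat to the trial's result. The documents do not support that: neither the definition of objective response nor the Simon boundaries (0 of 11 and 2 or fewer of 20) refers to these rows.

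**What to change.** Add one sentence to the hepatic section of Table 6-3: *When more than one hepatic row applies, the stricter action prevails; the Gilbert (direct bilirubin) qualifier and the hemolysis note continue to apply to the bilirubin row.*

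This settles all three differing cells. Capping the combined tier at bilirubin 3.0 x ULN would be less good, for three reasons:

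- The lower-band overlap would stay open.
- A hemolysis patient above 3.0 x ULN would have only the reduce-and-continue note, with no hold. Under the proposed sentence the combined tier's hold is kept: reduce one level if resolved within 7 days, otherwise discontinue.
- A Gilbert patient with total bilirubin above 3.0 x ULN but direct bilirubin no higher than 1.5 x ULN would meet no hepatic row. Under the proposed sentence the combined tier still covers that patient.

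The cost is one sentence in the next amendment. The downside is that a rare patient who recovers within 7 days from bilirubin > 3.0 x ULN loses the reduced-dose option, an outcome that the bilirubin row already prescribes.

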1.2.1.2.3 Conclusion of safety and efficacy in humans

Preliminary data obtained from the CBGJ398X2101 first in human trial indicate that the main safety findings in patients treated with BGJ398 (infigratinib) were as expected based on the preclinical studies: The on-target effects on calcium-phosphate homeostasis result in the observed increases in calcium, phosphorus, and creatinine, and not associated with clinical symptoms. In general, the increases have been mild to moderate in severity and manageable and reversible upon interruption or discontinuation of BGJ398 administration.

Ocular adverse events are frequent, but generally mild to moderate in severity and reversible. Corneal or retinal adverse events are recognized on ophthalmologic evaluations.

No effect of BGJ398 (infigratinib) on ECG intervals, including QTc has been noted. Reversible and largely asymptomatic decreases in LVEF have been noted in patients enrolled on study as measured by serial TTE or MUGA scans.

The preliminary efficacy signals were observed in multiple patients including patients with squamous cell histology.

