Neurotoxicity Grade 2 Grade ≥ 3	Omit dose of BGJ398 (infigratinib) until resolved to CTCAE Grade ≤ 1, then ↓ 1 dose level of BGJ398 (infigratinib) Discontinue patient from study drug treatment
GI disorders	
Pancreatitis Grade ≥ 2	Discontinue patient from study drug treatment

6.2 Worst Toxicity CTCAE v4.03 Grade (unless otherwise specified)	6.3 Recommended Dose Modifications any time during a cycle of therapy

Diarrhea
 
Grade 1
 
Grade 2
 
Grade 3
 
Grade 4
	
Maintain dose level of BGJ398 (infigratinib), but initiate anti-diarrheal treatment
 
 • Hold dose of BGJ398 (infigratinib) until resolved to CTCAE Grade \leq 1 • Optimize anti-diarrheal treatment, maintain dose level of BGJ398 (infigratinib). • For reoccurrence of diarrhea CTCAE Grade 2, hold dose of BGJ398 (infigratinib) until resolved to CTCAE Grade \leq 1, ↓ BGJ398 (infigratinib) by 1 dose level • Hold dose of BGJ398 (infigratinib) until resolved to CTCAE Grade \leq 1 • Optimize anti-diarrheal treatment • ↓ BGJ398 (infigratinib) by 1 dose level • For reoccurrence of diarrhea CTCAE Grade 3, despite optimal anti-diarrheal treatment, discontinue patient from study treatment. 
Discontinue patient from study treatment.
 
Note: Antidiarrheal medication is recommended at the first sign of abdominal cramping, loose stools or overt diarrhea

Vomiting
 
Grade 2 not controlled by optimal anti-emetic therapy
 
Grade 3 not controlled by optimal anti-emetic therapy or Grade 4
	
Hold BGJ398 (infigratinib) doses until \leq grade 1, ↓ 1 level
 
Discontinue patient from study

Eye Disorders (confirmed by ophthalmologic examination)	

Retinal disorders
 
Grade 2 CSR and CSR-like events
 
Grade 3 CSR and CSR-like events and any other grade 3 eye disorders
	
Hold BGJ398 (infigratinib) until resolved to \leq grade 1 but refer the patient to a retinal specialist for evaluation
 
 • If resolved in \leq 14 days, ↓ BGJ398 (infigratinib) by 1 dose level • If resolved in $>$ 14 days, discontinue BGJ398 (infigratinib) 
Hold BGJ398 (infigratinib) until resolved to grade \leq 1.
 
 • If resolved in \leq 14 days, ↓ BGJ398 (infigratinib) by 1 dose level • If resolved in $>$ 14 days, discontinue BGJ398 (infigratinib)

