6.2 Worst Toxicity CTCAE v4.03 Grade (unless otherwise specified)	6.3 Recommended Dose Modifications any time during a cycle of therapy
≥ grade 1 retinal vein occlusion, grade 4 CSR and CSR-like events, and grade 4 other eye disorders	Discontinue BGJ398 (infigratinib)
Other ocular/visual toxicity ≥ grade 3	Hold BGJ398 (infigratinib) until resolution to ≤ grade 1 If resolution in ≤14 days, ↓ 1 dose level, otherwise discontinue BGJ398 (infigratinib)
General disorders	
Fatigue Grade 3	Hold dose of BGJ398 (infigratinib) until resolved to CTCAE Grade ≤ 1 
 • If resolved in ≤ 7 days, maintain dose level of BGJ398 (infigratinib). • If resolved in > 7 days, discontinue patient from study treatment.
Other clinically significant AEs	
Grade 3	Hold dose of BGJ398 (infigratinib) until resolved to CTCAE Grade ≤ 1, then ↓ 1 dose level of BGJ398 (infigratinib).
Grade 4	Discontinue patient from study treatment.
All dose modifications should be based on the worst preceding toxicity. Once a dose has been reduced it will not be increased at a later time even if there is no toxicity. Patients who require more than two dose reductions of BGJ398 (infigratinib) will be discontinued from study drug treatment. If a patient requires a dose delay of > 14 days from the intended day of the next scheduled dose of BGJ398 (infigratinib) then study treatment must be stopped.	

Table 6-4 Toxicity – Follow-up evaluation

TOXICITY	FOLLOW-UP EVALUATION
Metabolic (hyperphosphatemia)	
Serum phosphorus lowering therapy consisting of dietary phosphate intake restriction and oral phosphate binders should be applied as follows:
 
Calcium-containing phosphate binders are not recommended.
 
Starting Cycle 1 Day 1 (beginning with the midday or evening meal on C1D1):
 
 - Restriction of dietary phosphate intake to 600 - 800 mg/day, if BMI ≥ 21kg/m². - Sevelamer 1 tablet (800mg) per meal; i.e. 3 x 800 mg/day.

TOXICITY	FOLLOW-UP EVALUATION

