6.7.5 Study drug discontinuation

Patients who discontinue study treatment should be scheduled for an End of Study Visit within 14 days after discontinuing study treatment, at which time all of the assessments listed for the End of study visit will be performed. Patients lost to follow up should be recorded as such.

All patients who discontinue study treatment (or a knowledgeable informant), including those who refuse to return for the final 14-day Follow up Visit, should be contacted for safety evaluations, anti-neoplastic therapies received after discontinuation of study drug, and overall survival \leq 30 days following the last dose of study treatment.

Patients whose treatment is interrupted or permanently discontinued due to a study-related adverse event or abnormal laboratory value must be followed 30 days post study discontinuation until all toxicities have resolved to CTCAE \leq 1 or until stabilization.

Patients whose treatment is interrupted or permanently discontinued due to any dose-limiting ocular/visual toxicity will have appropriate follow-up ophthalmologic examinations weekly until the toxicity has completely resolved or until the toxicity is considered to have stabilized after at least 6 months of follow-up. Refer to section on Clinical Safety.

	Screening	Treatment									Subsequent cycles	End of treatment / End of study visit	End of Post-treatment follow-up	Survival
		Cycle 1				Cycle 2				Cycle 3+ Visits on day 1 of each cycle unless more frequent visits are clinically indicated				
Visit no.	1 ¹	2	3	4	5	6	7	8	9	10+				
Day of cycle	Screening / Baseline	1	8	15	21	1	8	15	21	1		EOT*	End of Post-treatment follow-up	Survival**
Radiological tumor assessment/ response assessment (CT Scans) ⁴	X										Every uneven treatment cycle and +/- 8 days of D1 of respective cycle	X		
Hematology ⁵	X	X	X	X	X	X		X		X		X		
Serum Chemistry ⁶	X	X	X	X	X	X		X		X		X		
Pregnancy Test ⁷	X (blood)	X				X				X		X		
LVEF assessment ¹⁰	X	To be repeated every 4-6 months in asymptomatic patients. In symptomatic patients, LVEF assessment should be done every 2-4 months and more frequently as needed if symptoms occur/clinically indicated												
BGJ398 (infigratinib) dosing ⁸		Continuous (21 days with 7 days of rest)												
Tumor biopsy ⁹		In responders with progressive disease												
Prophylactic phosphate-lowering therapy		Daily												
Concomitant medications		Continuous monitoring												

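### Table 6-3 gives two opposite dosing instructions for a grade 4 non-retinal eye toxicity that resolves within 14 days

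*Combined protocol and SAP*

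**What the plan says.** The eye section of Table 6-3 (section 6.1.5) opens with a retinal block. Its grade 3 line reads "Grade 3 CSR and CSR-like events and any other grade 3 eye disorders" and calls for interruption, then a one-level reduction if the event settles within 14 days, otherwise discontinuation.

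Two further entries follow:

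- **Row A:** "≥ grade 1 retinal vein occlusion, grade 4 CSR and CSR-like events, and grade 4 other eye disorders". The action is to discontinue, with no route back to dosing.
- **Row B:** "Other ocular/visual toxicity ≥ grade 3". The action is to interrupt until grade 1 or lower, resume one dose level down if that takes no more than 14 days, and otherwise discontinue.

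At the end of the table, the entry for "Other clinically significant AEs" discontinues treatment at grade 4.

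The text of section 6.1.5 adds that if treatment has resumed at a lower dose and "the same toxicity recurs with the same or worse severity, the patient must discontinue study treatment".

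**The concern.** Row B's grade range includes grade 4, and Row A names grade 4 eye disorders other than retinal vein occlusion and CSR (the retinal event named in the table). A grade 4 non-retinal event therefore meets both descriptions. If it resolves quickly, Row A ends treatment and Row B resumes it.

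The trial is multicentre and remotely monitored (sections 4.1 and 13.5), so two sites could handle the same severe event in opposite ways, each following the table. Under Row B, the recurrence rule in section 6.1.5 would not by itself stop the drug if a grade 4 event came back at grade 3.

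Non-retinal eye toxicity is a recognised issue with this drug. Section 1.2.1.2.1 reports a corneal event among the dose-limiting toxicities at 150 mg and dry eye in 25.4% of patients in CBGJ398X2204. Section 5.2 excludes patients with current corneal disorders.

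**Working it through.** No sample-size or power figure is involved. The check compares the rows cell by cell, looks for a rule of precedence, and then sizes the problem.

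**1. The rows compared, for a non-retinal eye toxicity**

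| Grade | Falls to grade ≤ 1 | Grade 3 line / Row A | Row B | Agree? |
|---|---|---|---|---|
| 3 | within 14 days | resume one level lower | resume one level lower | yes |
| 3 | after 14 days | discontinue | discontinue | yes |
| 4 | after 14 days | discontinue | discontinue | yes |
| 4 | within 14 days | discontinue | resume one level lower | **no** |

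The conflict is confined to one cell.

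**2. Search for a tie-breaker**

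- The closing note of Table 6-3 bases modifications on the worst preceding toxicity. That selects the event to act on, not which of two rows applies to it.
- The resumption rule in section 6.1.5 refers the reader back to Table 6-3.
- The rule on delays beyond 14 days (section 6.1.5, the closing note and section 6.4) applies only where both rows already discontinue.
- Section 6.7.5 says patients whose treatment is interrupted or stopped for "dose-limiting ocular/visual toxicity will have appropriate follow-up ophthalmologic examinations weekly until the toxicity has completely resolved" or has stabilised after at least 6 months. This governs follow-up, not dosing.

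**3. What re-dosing would mean**

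By Table 6-2, Row B would restart a patient at 100 mg after 125 mg, or at 75 mg after 100 mg. A patient at 75 mg has used both reductions, so the rows differ there only if the 50 mg exception in section 6.1.5 is used.

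**4. How often this could arise**

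- Section 1.2.1.2.1 lists the grade 3 or 4 events reaching 5% in three single-agent studies (208 + 63 + 85 = 356 patients). No ocular term appears in any of the lists.
- Bound per ocular term, grades 3 and 4 combined: less than 5% × 20 = less than 1 patient in this trial.
- The documents give no grade 4 ocular rate. For an assumed rate *p* per patient and *n* = 20, the expected number is 20*p* and the chance of at least one event is 1 − (1 − *p*)^20:

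| Assumed *p* | Expected events | Chance of at least one |
|---|---|---|
| 0.5% | 0.1 | 1 − 0.995^20 = 9.5% |
| 1% | 0.2 | 1 − 0.99^20 = 18.2% |
| 2% | 0.4 | 1 − 0.98^20 = 33.2% |

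These figures count all grade 4 non-retinal eye events. The conflict needs the further condition of recovery within 14 days. The documents do not allow that fraction to be estimated, so the chance of meeting the conflict is lower.

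**The case against.** The best counter-argument is that Row A continues the retinal block. The table header repeats just before it, as at a page break, so the block may simply run from grade 2 to grade 3 to grade 4, with Row B then covering everything non-retinal. This reading gives each row something to do. On the broad reading, Row B duplicates the grade 3 line and contradicts Row A at grade 4. The reading is plausible, but the text does not state it. Row A speaks of eye disorders, the term that heads the whole section, and the grade 3 line above it is equally unrestricted.

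A second argument is that interrupting and reducing after a grade 4 event is normal in this table: neutropenia, haemoglobin and platelets all allow it. Those examples are haematologic. The non-haematologic rows whose rules reach grade 4 (AST/ALT, bilirubin unless due to haemolysis, creatinine, amylase/lipase, hypercalcaemia, neurotoxicity, diarrhoea, vomiting) discontinue. The catch-all for unlisted events does the same. It does not prove that Row B is the mistaken row, but it shows which way the table leans.

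Third, the column is headed as recommendations, and an investigator may remove a patient for an unacceptable event (section 6.6). Treatment also stops for a delay beyond 14 days or, under the closing note, a need for more than two reductions, so the recurrence rule is not the only brake. All of this is correct and limits the harm, as do the eye examinations in section 6.7.5 and the weekly safety teleconference in section 13.5. None of it says which row applies, and section 6.1.5 does require the guidelines to be followed.

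Finally, the event is rare, and section 1.2.1.2.3 says "Ocular adverse events are frequent, but generally mild to moderate in severity and reversible". That bears on priority, not on whether the instructions conflict.

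**Conclusion.** The concern holds. For a grade 4 non-retinal eye toxicity that falls to grade 1 or lower within 14 days, Table 6-3 gives two incompatible actions with no rule to choose between them. All other combinations of grade and timing agree.

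The practical size is small: 0.1 to 0.4 grade 4 events expected in 20 patients if the true rate lies in the assumed 0.5% to 2% range, and fewer that resolve in time. The consequence of any one event is re-exposure, or not, after a severe eye toxicity. The primary response-rate calculation is not affected. The point should be corrected, but it does not threaten the trial's conclusions.

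**What to change.** In Table 6-3, restrict Row B to grade 3 by removing the 'or higher' sign from its label. A grade 4 non-retinal event then leads to discontinuation on either reading of Row A: under Row A itself if that row is general, or under the grade 4 catch-all if Row A is retinal only. Grade 3 handling does not change.

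The cost is one label in the next amendment, with no added procedures or patients. The downside is that a patient whose grade 4 event clears quickly can no longer restart at a lower dose. If the investigators want to keep that option, the alternative is to limit Row A explicitly to retinal events. Either way, the table should state one rule.
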